3.5.2. ADVERSE EVENTS

Adverse events during the whole follow-up, per group, randomized allocation and grade:

- Number and proportion of participants with at least :
 - one AEFI
 - one AR
 - one SAE
- Number of following AEs:
 - Solicited or unsolicited adverse reaction from respiratory tract
 - AEFI with difficulties in breathing (asthma, spasmodic cough, pneumonia)
 - Cough
 - spasmodic cough
 - solicited systemic adverse event
 - unsolicited adverse event

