------------	--

Study title	Phase Ib (high dose), double-blind, single centre, dose-escalating, placebo-controlled, randomized study of a live attenuated B. pertussis strain given as a single intranasal dose to healthy adult volunteers
Study Identification Number:	C14-80
Sponsor	INSERM

	
Blood and nasopharyngeal samples for immunological assays.
 
Visit 5 (11±1 days after vaccination). Limited physical examination and measure of vital signs. Structured questionnaire concerning general and adverse events in the respiratory tract and a question about unsolicited adverse events. Nasopharyngeal aspiration for BPZE1 culture plating.
 
Visit 6 (14±1 days after vaccination). Limited physical examination and measure of vital signs. Structured questionnaire concerning general and adverse events in the respiratory tract and a question about unsolicited adverse events. Blood cell counts (haemoglobin, total and differential WBC, RBC, platelets). Nasopharyngeal aspiration for BPZE1 culture plating. Blood and nasopharyngeal samples for immunological assays.
 
Visit 7 (21 ±1 days after vaccination). Limited physical examination and measure of vital signs. Structured questionnaire concerning general and adverse events in the respiratory tract and a question about unsolicited adverse events. Nasopharyngeal aspiration for BPZE1 culture plating. Blood and nasopharyngeal samples for immunological assays.
 
Visit 8 (28 (-1; + 7) days after vaccination). Limited physical examination and measure of vital signs. Structured questionnaire concerning general and adverse events in the respiratory tract and a question about unsolicited adverse events. Subject diary collected and filed. Blood cell counts (haemoglobin, total and differential WBC, RBC, platelets). Females only, human chorionic gonadotropin (hCG). Nasopharyngeal aspiration for BPZE1 culture plating; If positive culture for BPZE1 after 4 weeks a new nasopharyngeal sample should be collected 2-3 weeks later for culture. Blood and nasopharyngeal samples for immunological assays.
 
Visit 8' (45 (-5; +10) days after vaccination). This visit will only be scheduled if BPZE1 was detected in the sample collected on the visit day 28. Limited physical examination and measure of vital signs. Questions concerning unsolicited adverse events. Nasopharyngeal aspiration for BPZE1 culture plating.
 
Visit 9 (6±1 months after vaccination). Questions concerning unsolicited adverse events. Limited physical examination and measure of vital signs. Blood cell counts (haemoglobin, total and differential WBC, RBC, platelets). Blood and nasopharyngeal samples for immunological assays.

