3. Collect blood samples as described in section XII.3. "*Blood samples*". Complete the appropriate document provided in the investigator or delegate Site file.
4. Collect nasopharyngeal aspirate as described in section XII.4. "*Nasopharyngeal samples*". Complete the appropriate document provided in the investigator or delegate Site file.
5. Arrange for an appointment for visit 8 (28 (-1; +7) days after visit 2)

VI.3.9. Visit 8, 28 (-1; +7) days after visit 2

During this visit the investigator or delegate will:

1. Collect and review the Diary. Check for any AEFI, interview on AR from the respiratory tract and systemic adverse events that might have occurred since visit 7, or any adverse event corresponding to the definition of a SAE (refer to Section XIII. "*Recording and reporting of adverse events*"), and check for any concomitant medication.
2. Perform a limited physical examination and measure blood pressure, heart rate, respiratory rate and record the information in the subject's CRF.
3. Collect blood samples as described in section XII.3. "*Blood samples*". Complete the appropriate document provided in the investigator or delegate Site file.
4. Collect nasopharyngeal aspirate as described in section XII.4. "*Nasopharyngeal samples*". Complete the appropriate document provided in the investigator or delegate Site file.
5. Collect urine sample from females and do a dip stick pregnancy testing.
6. Arrange for an appointment for visit 9 (6±1 months after visit 2).

VI.3.10. Visit 8', 45(-5; +10) days after visit 2

In case the nasopharyngeal aspirate contains detectable vaccine strain bacteria on day 28 the laboratory contacts the clinical investigator or delegate, who contacts the subject for a new visit.

During this visit the investigator or delegate will:

1. Collect information on any AEFI, interview on AR from the respiratory tract and systemic adverse events that might have occurred since visit 8, or any adverse event corresponding to the definition of a SAE (refer to Section XIII. "*Recording and reporting of adverse events*"), and check for any concomitant medication.
2. Perform a limited physical examination and measure blood pressure, heart rate, respiratory rate and record the information in the subject's CRF.
3. Collect nasopharyngeal aspirate as described in section XII.4. "*Nasopharyngeal samples*". Complete the appropriate document provided in the investigator or delegate Site file.

VI.3.11. Visit 9, 6±1months after visit 2

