During this visit the investigator or delegate will:

1. Collect information on any AEFI, interview on AR from the respiratory tract and systemic adverse events that might have occurred since visit 8 (or visit 8'), or any adverse event corresponding to the definition of a SAE (refer to Section XIII. "*Recording and reporting of adverse events*"), and check for any concomitant medication.
2. Perform a limited physical examination and measure blood pressure, heart rate, respiratory rate and record the information in the subject's CRF.
3. Collect blood samples as described in section XII.3. "*Blood samples*". Complete the appropriate document provided in the investigator or delegate Site file.
4. Collect nasopharyngeal aspirate as described in section XII.4. "*Nasopharyngeal samples*". Complete the appropriate document provided in the investigator or delegate Site file.
5. Complete the End of study section in the CRF.

VI.4. SCREENING NUMBER AND RANDOMIZATION PROCEDURE

Subject

At visit 1 after a signed and dated ICF has been obtained from the subject, each subject will be assigned a **unique screening number** consisting of 3 digits (for example, 001) and the initials of the subject consisting of 3 letters (for example ATA for Anders Tomas Andersson). In case of no middle name there should be a hyphen in the middle (for example S-S for Sven Svensson).

If the consent to participate in the study is withdrawn before randomization at Visit 2, Day 0, this screening number will be kept and **not reassigned** to another subject, for any reason.

Randomization procedure and blinding

Vaccine and placebo will come in identical, coded vials.

The vials will be coded with group number and vial number: group1: 101 – 116, group 2: 217 – 232, group 3: 333 – 348 and group 4: 449 -454, for the respective groups described above under point VI.2 "General study plan and design".

To ensure randomized allocation, the vials must be used by the site in their consecutive order of vial numbers within a given dose group. The vial number **given to the volunteer (and the time of administration)** will be recorded both in the CRF and the medical record (source data).

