- The study may be stopped if a volunteer within the period 0-28 days after vaccination suffers from clinical whooping cough without laboratory demonstration of wild-type *B. pertussis*. In such a case it must be suspected that the symptoms are caused by BPZE1.
- The study may be stopped if a volunteer has a SAE which is considered by the DSMB to be most probably caused by BPZE1.

At the regular DSMB meetings before the start of dose group 2 and 3, respectively, the DSMB will review all accumulated safety data in the trial (AEs and SAEs per dose and randomized allocation) and make a recommendation whether the next higher dose can be administered.

A DSMB charter will describe the functioning of the DSMB.

XIV. Endpoints

XIV.1. PRIMARY SAFETY ENDPOINT

The primary safety endpoint will be the number and proportion of participants, per dose group and randomized allocation, with at least one of the following adverse events between Day 0 (Visit 2) and Day 28 (Visit 8):

- Cough and spasmodic cough of grade 2 or higher.
- Other respiratory tract AE related or possibly related to vaccination of grade 3 or higher.
- Any other AE related or possibly related to vaccination of grade 3 or higher.

XIV.2. SECONDARY SAFETY ENDPOINT

The second safety endpoint will be the number and proportion of participants per dose group and randomized allocation, with:

- at least one episode of cough or spasmodic cough, described by grade, between Day 4 and Day 28
- at least one solicited or unsolicited AEFI from respiratory tract between Day 0 and Day 28
- at least one AEFI with difficulties in breathing (asthma, spasmodic cough, pneumonia) between Day 0 and Day 28
- at least one other AEFI from the respiratory tract between Day 0 and Day 28
- at least one episode of cough, described by grade, between Day 0 and Day 28
- at least one episode of spasmodic cough, described by grade, between Day 0 and Day 28
- at least one solicited systemic AEFI between Day 0 and Day 28 (fever, headache, tiredness)
- at least one unsolicited AEFI between Day 0 and Day 28

Adverse events following immunization (AEFI) should be reported at study visits during the first 28 days of the concerned subject.

Serious adverse events (SAE) should be reported immediately but no later than 24 hours after detection. AEFI which lead to difficulties in breathing (asthma, spasmodic cough, pneumonia) will be considered as serious and reported to the Data Safety Monitoring Board (DSMB) and the sponsor.

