2.1.1. PRIMARY SAFETY ENDPOINT

- **Definition**

The primary safety endpoint will be the number and proportion of participants, per dose group and randomized allocation, with at least one of the following adverse events between Day 0 (Visit 2) and Day 28 (Visit 8):

- Cough and spasmodic cough of grade 2 or higher.
- Other respiratory tract AE related or possibly related to vaccination of grade 3 or higher.
- Any other AE related or possibly related to vaccination of grade 3 or higher.

- **Strategy for the main analysis**

The main analysis is conducted:

- By modified intention to treat: This means that all randomized participants who received a vaccine dose are included in the analysis in the group to which they were initially randomized and all their data is used regardless of protocol deviations during the trial/study.
- In this analysis, participants with missing follow-up data will be assumed to be event-free, unless the site has any knowledge of a safety event having occurred and has notified this in the e-CRF.

- **Strategy for secondary analyses**

- With the strategy of *definitely missing follow-up data (i.e. premature termination of follow-up) = failure*.
(For non-compliant participant, it will be assumed that no safety event occurred during the missing visits)

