3.8. OTHER SECONDARY ENDPOINTS

1) Colonization of the BPZE1 strain in the nasopharyngeal mucosa:

Per dose, group and randomized allocation:

- Number and proportion of participants who have been colonized by the modified *B. pertussis* strain BPZE1 at each time point
- Number of days during which bacteria are detected
- Quantity of bacterial colonization (number of cfu) per post-vaccination visit
- Cough, spasmodic cough and any symptom from the respiratory tract will be described for colonized and not colonized participants

2) Immunogenicity:

Per dose, group, colonized/not colonized and randomized allocation:

- IgG and IgA antibodies against PT, FHA, PRN, and fimbriae 2/3 in serum at visits 2, 4, 6, 7, 8, 9 and 10
 - Geometric mean levels and 95%CI for pre and post vaccination (expressed in IU/mL calibrated against reference antisera from the National Institute for Biological Standards and Controls)

- Participants with positive responses (n, % and 95%CI), defined by at least 100% increase from pre- to post-vaccination, to at least 4 times MLD after vaccination (n, % at each post-vaccination time point)

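### Tables with no time window mix routine follow-up with an extra adverse-event interview (Visit 8') held only for volunteers still culture-positive at Day 28

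*Combined protocol and SAP*

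**What the plan says.** **Who attends Visit 8'.** The protocol synopsis states: "This visit will only be scheduled if BPZE1 was detected in the sample collected on the visit day 28". Section VI.3.10 has the investigator or delegate examine these volunteers, take another culture and "interview on AR from the respiratory tract and systemic adverse events that might have occurred since visit 8". Under the exceptions in protocol II.3, the laboratory tells the investigator about the positive culture so that the visit can be arranged.

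**What everyone else has.** The diary runs from Day 0 to Day 28 (protocol XIII.2). The next scheduled contact is Visit 9 at Month 6±1. It covers "systemic adverse events that might have occurred since visit 8 (or visit 8", where the last words refer to Visit 8' for those who attended it (VI.3.11).

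**What is tabulated.**
- SAP 3.5.2 covers "Adverse events during the whole follow-up, per group, randomized allocation and grade". It lists participants with at least one AEFI, AR or SAE, and counts of cough, spasmodic cough and other event types. It gives no period split and no rule for Visit 8'.
- SAP 2.1.3 and 3.8 add: "Cough, spasmodic cough and any symptom from the respiratory tract will be described for colonized and not colonized participants". No window is given.
- For colonization, SAP 3.8 asks for the proportion colonized at each time point and "Quantity of bacterial colonization (number of cfu) per post-vaccination visit". SAP 2.1.3 counts the visits with bacteria detected; 3.8 counts days. None of these has a Day-28 limit or a denominator, although the colonization objective in SAP 1.1.2 is confined to 28 days.

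**What already stops at Day 28.** The primary endpoint (SAP 2.1.1), all the secondary safety endpoints in SAP 2.1.2, and the interim analysis for Phase II design (SAP 2.1.6).

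**The concern.** Attendance at Visit 8' depends on a post-vaccination result that is tied to allocation. Placebo is the diluent alone, and protocol III.3 reports no cross-contamination between volunteers in the earlier trial, so attendees should be vaccinees.

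Attendees are asked about the weeks after Day 28 while memory is fresh. Everyone else is asked about the same weeks some five months later. The interviewing team also knows that the attendee carries the vaccine strain. That matters because SAP 3.5.2 counts adverse reactions, and these rest on a judgement of relatedness (protocol XIII.1).

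The colonized/non-colonized description is the most exposed output, because colonization itself triggers the extra questioning. It bears on a question that protocol III.2 calls crucial: whether a dose that colonizes most vaccinees still causes no whooping-cough symptoms.

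**Working it through.** **The plan's own figures.** The documents give no figure for late events or for Visit 8'. The sample-size statements (SAP 1.3) concern the Day 0-28 endpoint, and they reproduce:
- 1 − (1 − 0.126)^12 = 0.801, stated as 80%.
- Upper 95% bound for 0/12: 1 − 0.025^(1/12) = 26.5%, stated as 26%.
- Upper 95% bound for 0/36: 1 − 0.025^(1/36) = 9.7%, stated as 10%.

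None of these depends on Visit 8'.

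**Timing.** Visit 8 falls on Day 27-35 and Visit 8' on Day 40-55. The gap is nominally 45 − 28 = 17 days and can range from 40 − 35 = 5 to 55 − 27 = 28 days.

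**Arm-level effect on late events.** Let k of 12 vaccinees attend. Let r1 be the probability that a post-Day-28 event is reported without the extra interview, and r2 the probability with it. The excess over placebo in the vaccine arm is (k/12)(r2 − r1), which is k(r2 − r1) participants. All values of k, r1 and r2 are assumptions.

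| k | r1 = 0.20, r2 = 0.30 | r1 = 0.30, r2 = 0.45 | r2 = r1 |
|---|---|---|---|
| 2 | 1.7 points (0.2 participants) | 2.5 points (0.3) | 0 |
| 4 | 3.3 points (0.4) | 5.0 points (0.6) | 0 |
| 6 | 5.0 points (0.6) | 7.5 points (0.9) | 0 |

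**A second route.** Assume a 10% weekly background of respiratory symptoms.
- Probability of a symptom in the 17 days: 1 − 0.9^(17/7) = 0.226.
- Captured at Visit 8', if 90% are reported: 0.226 × 0.9 = 0.203.
- Captured at Month 6, if 30% to 70% are recalled: 0.068 to 0.158.
- Difference per attendee: 4.5 to 13.5 points. With 2 of 12 attending, × 2/12 = 0.75 to 2.25 points, or about 0.1 to 0.3 of a participant.

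**At least one AEFI over the whole follow-up.** If 80% already have an event by Day 28, only the remaining 20% can change status. With r1 = 0.30 and r2 = 0.45 the excess is 0.20 × 0.15 × k/12, which is 0.5, 1.0 and 1.5 points for k = 2, 4 and 6.

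**Colonized versus not colonized.** With c colonized, of whom k attend, the excess in the colonized row is (k/c)(r2 − r1). For c = 6, k = 2 and r2 − r1 = 0.15 it is 5.0 points. If every colonized volunteer is still positive at Day 28 (k = c), it is the full 15 points.

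**Colonization at Visit 8'.** Suppose 4 of 12 are positive at Day 28 (33.3%) and 2 of them remain positive.
- On those sampled: 2/4 = 50%, above the Day-28 figure.
- On the arm: 2/12 = 16.7%, which is not inflated but treats the unsampled as negative.
- Scheduled cultures number 6 (Visits 3-8) for most volunteers and 7 for attendees. Here the seventh adds 2/12 = 0.17 positive visits per person, or 4/12 = 0.33 if all four stay positive.

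**The case against.** A reader might infer that the plan demonstrably inflates both adverse events and colonization in colonized vaccinees, and so biases the vaccine-placebo contrast. The documents do not support that.

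- **No interval goes unasked.** Visit 9 covers the same period for everyone. Volunteers are also told to contact the investigator at once about serious events or visits to another physician (VI.3.3), and SAEs are reportable within 24 hours whatever the visit. What remains is a difference in recall, in the number of contacts and in the interviewer's knowledge, mainly for non-serious events.
- **Systematic collection ends early.** The protocol says: "Adverse events following immunization (AEFI) should be reported at study visits during the first 28 days of the concerned subject". Late non-serious events are therefore secondary. Even so, Visits 8' and 9 collect them and SAP 3.5.2 tabulates them.
- **Only Day-28 positives are affected.** Colonized volunteers who cleared earlier are followed exactly like placebo recipients.
- **The main safety outputs are already limited to Day 28,** and SAP 2.2.2 rules out statistical comparisons between arms. This stands in full: the exposure is confined to descriptive tables.
- **Colonization.** The SAP is silent on the denominator. Restricting the endpoint to 28 days is a natural reading of the objective, and SAP 2.2.1 reports the amount of available data for each variable.

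A ratio is also tempting: 0.203/0.158 = 1.3 up to 0.203/0.068 = 3.0. It describes only attendees and only events in the nominal Day 28-45 interval, on assumed rates. It is not an effect on any row of SAP 3.5.2.

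What the objection does not remove is that two SAP descriptions have no window and no rule for a visit triggered by colonization.

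**Conclusion.** The concern holds as a limited point about descriptive tables. As written, SAP 3.5.2 and the colonized/non-colonized symptom description combine ordinary follow-up with questioning triggered by a positive culture and done with knowledge of it. Late events in Day-28-positive vaccinees can be overstated as a result.

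The likely direction is upward. The size is unknown, is zero if Month-6 recall is complete, and is probably a fraction of one participant per 12-person arm: about 0.1 to 0.9 in the scenarios above, where one participant is 8.3 points. Those scenarios rest on assumed attendance and reporting rates, none of which the documents give. The proportion affected can be larger in the colonized row, where the denominator is smaller.

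Colonization is overstated only if Visit 8' is expressed on those sampled. The defect there is an unstated denominator and an unstated last visit, not a demonstrated inflation.

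**What to change.** Change the SAP as follows:
- **2.1.3 and 3.8, symptoms by colonization status:** restrict to onset on Day 0-28.
- **3.5.2:** split events into Day 0-28, Day 29 to Month 6, and Month 6 to Month 12. The last period applies to groups 1-3 only, since SAP 1.1.2 follows group 4 for 6 months. Flag events first elicited at Visit 8'.
- **2.1.3 and 3.8, colonization:** limit the per-visit proportion, the cfu tables and the count of positive visits to Visits 3-8, in line with the 28-day objective.
- **Visit 8':** list separately as the number still positive over the number positive at Day 28, with the number vaccinated in the arm also shown.

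This costs SAP wording and table shells. It needs no new data and drops no event. The downside is that late events appear in a separate table.

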3.6. PRIMARY SAFETY ENDPOINT

The primary endpoints (see definition in chapter 2.1.1) will be described per group and randomized allocation (n, %, and 95% confidence interval).

Each individual component of the primary endpoint will also be described:

- Participants with at least one occurrence of cough or spasmodic cough of grade 2 or higher between Day 0 and Day 28 (n, %, 95% CI)
- Participants with at least one other respiratory tract AE related or possibly related to vaccination of grade 3 or higher between Day 0 and Day 28 (n, %, 95% CI)
- Participants with at least one other AE related or possibly related to vaccination of grade 3 or higher between Day 0 and Day 28 (n, %, 95% CI)

3.7. SECONDARY SAFETY ENDPOINT

Per group and randomized allocation:

- at least one episode of cough or spasmodic cough, described by grade, between Day 4 and Day 28
- at least one solicited or unsolicited adverse reaction from respiratory tract between Day 0 and Day 28
- at least one AEFI with difficulties in breathing (asthma, spasmodic cough, pneumonia) between Day 0 and Day 28
- at least one other AEFI from the respiratory tract between Day 0 and Day 28
- at least one episode of cough, described by grade, between Day 0 and Day 28
- at least one episode of spasmodic cough, described by grade, between Day 0 and Day 28
- at least one solicited systemic AEFI between Day 0 and Day 28 (fever, headache, tiredness)
- at least one unsolicited AEFI between Day 0 and Day 28

